#### **5.4.1.1.2. Treatment Failure**

A participant will be defined as off-treatment failure if he/she never had HBsAg seroclearance 24 weeks after stopping all study interventions at the end of the consolidation phase and without restarting NA treatment.

#### **5.4.1.1.3. Thresholds of HBV RNA and HBcrAg Levels**

Thresholds for **HBV RNA values**:

- TND
- $<$  LOD
- $<$  LLOQ
- $< 1000$  IU/mL

Thresholds for **HBV RNA decreases from baseline**:

- $\geq 1 \log$  IU/mL
- $\geq 2 \log$  IU/mL
- $\geq 3 \log$  IU/mL
- $\geq 4 \log$  IU/mL
- $\geq 5 \log$  IU/mL

Thresholds for **HBcrAg values**:

- $<3.0 \log$  U/mL
- $<4.0 \log$  U/mL

Thresholds for **HBcrAg decreases from baseline**:

- $\geq 1 \log$  IU/mL
- $\geq 2 \log$  IU/mL

- $\geq 3$  log IU/mL
- $\geq 4$  log IU/mL
- $\geq 5$  log IU/mL
- $\geq 6$  log IU/mL

#### **5.4.1.1.4. Thresholds Based Multiple Markers for participants who completed NA Treatment**

**Thresholds based on multiple markers:**

- **HBsAg<LLOQ and HBV DNA**
  - HBsAg<LLOQ and HBV DNA<LLOQ\*\*
  - HBsAg < LLOQ and HBV DNA < LLOQ for target detected
  - HBsAg < LLOQ and HBV DNA < LLOQ for target not detected
  - HBsAg<LLOQ and HBV DNA $\geq$ LLOQ
- **HBsAg $\geq$ LLOQ and HBV DNA<2,000 IU/ml**
  - HBsAg $\geq$ LLOQ and HBV DNA<LLOQ\*\*
  - HBsAg  $\geq$  LLOQ and HBV DNA < LLOQ for target detected
  - HBsAg  $\geq$  LLOQ and HBV DNA < LLOQ for target not detected
  - HBsAg  $\geq$  LLOQ and HBV DNA < LLOQ for target detected and not detected
  - HBsAg  $\geq$  LLOQ and LLOQ  $\leq$  HBV DNA < 2,000 IU/mL
  - HBsAg  $\geq$ LLOQ and HBV DNA <2,000 IU/mL
  - HBsAg $\geq$ LLOQ and LLOQ  $\leq$ HBV DNA<2,000 IU/ml
- **HBsAg $\geq$ LLOQ and HBV DNA $\geq$ 2,000 IU/ml**
  - HBsAg<100 IU/mL and HBV DNA $\geq$ 2,000 IU/ml
  - HBsAg $\geq$ 100 IU/mL and HBV DNA $\geq$ 2,000 IU/ml
  - HBsAg  $\geq$ LLOQ and HBV DNA  $\geq$ 2,000 IU/mL
  - HBsAg <100 IU/mL and HBV DNA < LLOQ
  - HBsAg <100 IU/mL and HBV DNA $\geq$ 2,000 IU/mL
  - HBsAg  $\geq$  100 IU/mL and HBV DNA  $\geq$  2,000 IU/ml
  - HBsAg <100 IU/mL and HBV DNA < 2000 IU/ml

\*\* HBV DNA<LLOQ will be summarized by DNA target detected, TND and overall.

Due to the exploratory objectives of this Phase 2 study, additional blood marker reduction/seroclearance thresholds may be added at a later point in time according to the clinical interest.

#### **5.4.1.1.5. Anti-HBe Antibodies**

Participants who have positive and negative Anti-HBe values will be evaluated over time.

#### **5.4.1.2. Values and Change Over Time Endpoints**

##### **5.4.1.2.1. HBV RNA and HBcrAg**

Actual values and changes from baseline (log transformed value) over time in HBV RNA, and HBcrAg will be evaluated.

Change will be defined as: value at a given time point minus baseline value.

The change from baseline value to nadir (i.e., maximum decrease for each participant) in HBV RNA and HBcrAg will be evaluated at three intervals: on-treatment nadir, during follow-up nadir, and entire study duration nadir by met the NA treatment completion criteria and stopped NA or did not meet and did not stop NA.

##### **5.4.1.2.2. Anti-HBs Antibodies**

Actual values and change from baseline will be evaluated over time when anti-HBs antibodies are assessed.

Change from baseline is defined as: value at a given time point minus baseline value. Participants who have positive and negative Anti-HBs values will be evaluated over time.

##### **5.4.1.2.3. Liver Stiffness Measurements**

Severity of liver disease at the end of study intervention and follow-up versus baseline will be evaluated by the actual values and changes in fibrosis according to Fibroscan liver stiffness measurements. Change will be defined as: value at a given time point minus baseline value.

#### **5.4.1.3. Endpoints for Correlation**

##### **5.4.1.3.1. Association between several endpoints after the beginning of the consolidation phase**

Correlations between the following endpoints will be evaluated for participants who received at least one dose of Pegylated Interferon:

- Maximum ALT increase (U/L) vs Maximum HBV DNA increase (log10 IU/mL) between Consolidation Baseline and FU Week 4
- Maximum ALT increase (U/L) vs Maximum Neutrophils ( $10^9/L$ ) decrease between Consolidation Baseline and FU Week 4

- Maximum ALT increase (U/L) vs Maximum HBsAg decrease ( $\log_{10}$  IU/mL) between Consolidation Baseline and FU Week 4
- Additional HBsAg decline ( $\log_{10}$  IU/mL) at CW12 vs Maximum Neutrophils decrease between Consolidation Baseline and FU Week 4
- Additional HBsAg decline ( $\log_{10}$  IU/mL) at CW12 vs Maximum ALT increase (U/L) between Consolidation Baseline and FU Week 4

To evaluate the additional HBsAg decline ( $\log_{10}$  IU/mL) at CW12, a linear regression model using the four last HBsAg measures before Consolidation Baseline is performed to estimate Predicted value of HBsAg at CW12.

## 5.4.2. Analysis Methods

Statistical analyses of all exploratory endpoints will use descriptive statistics. Treated analysis set will be used. The selected exploratory endpoints efficacy analyses will use combining the data from participants who received PegIFN- $\alpha$ 2a but not JNJ-6379 in Cohort 1 with data of Cohort 2, the PegIFN- $\alpha$ 2a ITT analysis set will be used. If applicable, additional statistical analyses (descriptive statistics and spaghetti plots) may be added for each of the following subgroups: participants who received at least one dose of JNJ-6379 and an induction phase duration  $\leq$ 36 weeks, participants who received at least one dose of JNJ-6379 and an induction phase duration  $>$ 36 weeks, participants who never received JNJ-6379. The mTreated and mPegIFN- $\alpha$ 2a ITT will be used if relevant difference between the sets exists (see Section 2.3).

### 5.4.2.1. Binary Endpoints

Please see the section 5.3.2.1.

#### 5.4.2.1.1. Treatment Failure

The number and proportion of off-treatment failure participants, as defined in Section 5.4.1.1.2, will be summarized descriptively by cohort.

#### 5.4.2.1.2. Thresholds based on HBV RNA and HBcrAg Levels

The number and proportion of participants achieving the cut-offs as defined 5.4.1.1.3 will be summarized by cohort and analysis phase over time.

Cumulative percentage of participants achieving any given decrease from baseline in HBV RNA and HBcrAg respectively at the end of induction, end of consolidation, and all FU time points, separately, will be presented graphically.

#### 5.4.2.1.3. Anti-HBe Antibodies

The number and proportion of participants having anti-HBe positive/negative values will be summarized by cohort and analysis phase over time.

Shift tables in anti-HBe positive/negative values from baseline will be provided at each time point.

#### **5.4.2.1.4. Thresholds Based Multiple Markers for participants who completed NA Treatment**

The number and proportion of participants who meet the blood marker reduction/seroclearance thresholds at all FU time points, respectively, after stopping all study interventions (including NA) and not having NA re-treated will be summarized descriptively by cohort for each marker and each threshold listed in Section 5.4.1.1.4.

#### **5.4.2.2. Values and Change Over Time Endpoints**

##### **5.4.2.2.1. HBV RNA and HBcrAg**

The values of and changes from baseline in HBV RNA and HBcrAg, respectively, will be summarized only descriptively over time in a similar manner as for values and changes from baseline over time in HBsAg, and HBV DNA as described in Section 5.3.2.2.1, including the change from baseline value to nadir (i.e., maximum decrease for each participant) and the various graphical displays.

Only the participants with HBV RNA values  $\geq \text{LOD} + 0.5 \log_{10} \text{cp/mL}$  (i.e.,  $\geq 2.99 \log_{10} \text{cp/mL}$ ) at baseline will be included in this analysis. Similarly, additional analyses only for participants with HBV RNA values  $\geq \text{LOD} + 1.0 \log_{10} \text{cp/mL}$  and  $\geq \text{LOD} + 2.0 \log_{10} \text{cp/mL}$ , respectively, will be summarized.

Only the participants with HBcrAg values  $\geq \text{LLOQ} + 0.5 \log_{10} \text{U/mL}$  (i.e.,  $\geq 3.5 \log_{10} \text{U/mL}$ ) at baseline will be included in this analysis.

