**Table 4: Data Handling Rules for HBV Virology and Serology Assessments**

HBV parameter	LLOQ	ULOQ	Imputed Values	
			If value < LLOQ	If value > ULOQ
HBsAg	0.05 IU/mL	249,750.00 IU/mL with dilution	0.025 IU/mL (a)	274,725.00 IU/mL (b) with dilution
HBeAg	0.11 IU/mL	7,000.00 IU/mL with dilution	0.055 IU/mL (a)	7,700.00 IU/mL (b) with dilution
HBcrAg*	3.0 log 10 U/mL	7.0 log 10 U/mL w/o dilution 9.0 log 10 U/mL with dilution	2.7 log 10 U/mL	7.7 log 10 U/mL (b)(c) w/o dilution 9.9 log 10 U/mL (b) with dilution
HBV DNA	20 IU/mL	170,000,000 IU/mL w/o dilution	If target detected: 15 IU/mL If target not detected: 5 IU/mL**	187,000,000 (b)(c) IU/mL w/o dilution
HBV RNA*	LLOQ = 2.939 log 10 cp/mL (i.e., 869 cp/mL) LOD = 1.398 log 10 cp/mL	NAP	If <LOD or target not detected then 1.114 log 10 cp/mL (i.e., 13 cp/mL)	NAP

HBV parameter	LLOQ	ULOQ	Imputed Values	
			If value < LLOQ	If value > ULOQ
	(i.e., 25 cp/mL)			
Anti-HBs	5 mIU/mL	10000.0 mIU/mL	2.5 mIU/mL (a)	11000.0 mIU/mL (b)

\* As new assays become available different data handling rules may apply.

\*\* For HBV DNA <LLOQ: Spaghetti plots showing absolute values, the imputed value will be 15 IU/mL for both target detected and target not detected. All other tables, listings and figures, will be produced using 15 IU/mL as an imputed value if target is detected and 5 IU/mL if target is not detected.

Key: NAP=Not applicable

- (a) LLOQ/2
- (b) ULOQ+(ULOQ/10)
- (c) If the original result > ULOQ, then take the re-test value (i.e., diluted result). If the diluted result is not available, use the imputed value indicated in this table

All other viral activity data with values <LLOQ which are not included in the data handling rules above will be imputed by the absolute value divided by 2.

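### The HBV RNA baseline cut-off is printed as 2.99 log10 cp/mL, but the SAP's own LOD plus 0.5 gives 1.898, so the analysis set is ambiguous

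*SAP*

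**What the plan says.** SAP Section 5.4.2.2.1 covers values of, and changes from baseline in, HBV RNA and HBcrAg. For HBV RNA, "Only the participants with HBV RNA values" at baseline of at least LOD + 0.5 log10 cp/mL enter the analysis, and a bracketed gloss gives that threshold as 2.99 log10 cp/mL. The next sentence adds analyses restricted to baseline values of at least LOD + 1.0 and at least LOD + 2.0, without numbers. The HBcrAg rule that follows is LLOQ + 0.5, glossed as 3.5 log10 U/mL.

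SAP Table 4 supplies the assay limits. Its HBV RNA row gives "LLOQ = 2.939 log"10 cp/mL (869 cp/mL) and an LOD of 1.398 log10 cp/mL (25 cp/mL). The only imputed value in that row, 1.114 log10 cp/mL (13 cp/mL), applies to results below the LOD or with target not detected. A sentence under the table says that viral activity results below LLOQ that the table does not cover are halved. A footnote on the HBV RNA and HBcrAg rows reads "As new assays become available different data handling rules may apply".

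**The concern.** The rule and its printed number disagree, and the SAP does not say which one the programmer should follow. The choice decides who contributes to the HBV RNA change-from-baseline summaries, the stated exploratory endpoint for this marker (SAP Section 1.1).

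The additional sets make this worse. They are written only as LOD plus an increment, so their cut-offs depend on the LOD used. A programmer could reasonably take the printed 2.99 for the main set and Table 4's LOD for the other two. A participant could then be in an additional set meant to be stricter while being left out of the main one.

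**Working it through.** **Inputs.** From Table 4: HBV RNA LOD 1.398 log10 (25 cp/mL), LLOQ 2.939 log10 (869 cp/mL), imputed value below LOD 1.114 log10, HBcrAg LLOQ 3.0 log10 U/mL. From Section 5.4.2.2.1: increments of 0.5, 1.0 and 2.0, and printed cut-offs of 2.99 (HBV RNA) and 3.5 (HBcrAg).

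**Is Table 4 internally consistent?** Yes: log10(25) = 1.398 and log10(869) = 2.939.

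**Can 2.99 be reproduced?**
- LOD + 0.5 = 1.398 + 0.5 = 1.898
- LLOQ + 0.5 = 2.939 + 0.5 = 3.439
- Imputed below-LOD value + 0.5 = 1.114 + 0.5 = 1.614
- Addition on the copy scale: log10(25 + 10^0.5) = 1.450

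None gives 2.99. Working back, 2.99 − 0.5 = 2.49 log10, about 309 cp/mL, which neither document gives as a limit. The HBcrAg gloss does reproduce (3.0 + 0.5 = 3.5), so the bracketed numbers are meant as plain arithmetic.

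**Size of the gap.** 2.99 − 1.898 = 1.092 log10, and 10^1.092 = 12.4. In copies, 10^1.898 = 79 and 10^2.99 = 977 cp/mL.

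**Do the three sets nest?**

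| Coding choice | Main | LOD + 1.0 | LOD + 2.0 | Nested? |
|---|---|---|---|---|
| Table 4 LOD (1.398) throughout | 1.898 | 2.398 | 3.398 | Yes |
| Implied LOD (2.49) throughout | 2.99 | 3.49 | 4.49 | Yes |
| Printed 2.99 for main, Table 4 LOD for the rest | 2.99 | 2.398 | 3.398 | No |

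In the mixed case, a participant with baseline HBV RNA from 2.398 to below 2.99 log10 (250 to below 977 cp/mL) is in the LOD + 1.0 set but not the main set. The LOD + 2.0 set still lies inside the main set.

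**Results between LOD and LLOQ.** Both 1.898 and 2.398 lie below the LLOQ of 2.939, so the value given to a detected but unquantified result matters. If the general halving rule applies and means LLOQ/2 in copies, the value is log10(869/2) = 2.638. Such a result passes both 1.898 and 2.398, so the main and LOD + 1.0 sets contain the same people, and it fails 2.99. If the log10 value were halved instead, 2.939/2 = 1.47, and it fails every cut-off. The SAP does not say which reading is meant for HBV RNA.

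**The case against.** The best defence is that Section 5.4.2.2.1 writes all three cut-offs in the same form, as LOD plus an increment, so a programmer would naturally use one LOD throughout and the sets would nest. That stands. A reader might infer that the planned sets are simply not nested. The documents support this only for the mixed coding, and then only for the LOD + 1.0 set.

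A reader might also infer that Table 4 leaves results between LOD and LLOQ without a value. That goes too far, because the halving sentence under the table may cover them. What remains is that its application to HBV RNA is not stated.

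The footnote on new assays leaves room for 2.99 having come from another assay. The documents therefore cannot show whether 2.99 or 1.398 is the outdated figure. Either way, the two places still disagree.

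Finally, the practical effect may be slight. Participants must be HBeAg positive with HBV DNA of at least 20,000 IU/mL at screening, and the SAP's Amendment 2 log reports every participant above 4 log10 for baseline HBcrAg. Both suggest, without proving, that few have baseline HBV RNA below 977 cp/mL. The summaries are descriptive, no formal test is planned (SAP Section 5.1.1), and the Schedule of Activities allows HBV RNA testing of selected samples only. This limits the weight of the point but does not remove the contradiction.

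**Conclusion.** The inconsistency is certain on the documents' own figures: the rule gives 1.898 log10 cp/mL and the printed number is 2.99, a 1.092 log10 (12.4-fold) difference in an inclusion threshold. Loss of nesting is a conditional consequence, arising only if the printed figure and Table 4's LOD are mixed.

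How many participants have baseline HBV RNA between 79 and 977 cp/mL is not in the documents. The baseline table planned in SAP Section 4.2.2, with categories for below LOD, below LLOQ and below 1,000 copies/mL, should give a rough count. The point concerns an exploratory, descriptive analysis and does not touch the primary endpoint. It is worth correcting because it defines an analysis set and is cheap to settle.

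**What to change.** Confirm the LOD of the HBV RNA assay actually used, and make Table 4 and Section 5.4.2.2.1 agree with it. Print all three cut-offs from that single LOD: 1.898, 2.398 and 3.398 log10 cp/mL if Table 4 is right. If an LOD of 2.49 is right, correct Table 4 and print 2.99, 3.49 and 4.49.

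State whether the general halving rule applies to HBV RNA results between LOD and LLOQ and, if so, which quantity is halved and on which scale.

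Moving the rule to LLOQ + 0.5, by analogy with HBcrAg, is not needed. It would change the SAP's anchor, and at 3.439 the main set would be stricter than the SAP's own LOD + 2.0 set at 3.398 (Table 4 LOD). Table 4 lists no LOD for HBcrAg, so the analogy is weak.

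The cost is a few words in the SAP and a check of the programmed cut-offs, with no new data.

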##### **5.4.2.2.2. Anti-HBs Antibodies**

The values of and changes from baseline in anti-HBs antibodies will be summarized only descriptively in a similar manner as described for values and changes from baseline over time in other blood disease markers in Section 5.3.2.2.1.

Additionally, for all ITT participants with positive anti-HBs antibodies at baseline who will reach HbsAg seroclearance (as defined in Section 5.3.1.1.3), descriptive statistics will be calculated for the change of anti-HBs antibodies level from baseline at the timepoint when achieving the HbsAg seroclearance by cohort. In an additional summary, the change of anti-HBs antibodies level from baseline at the specific timepoint (i.e., Week 12 of the consolidation phase, FU Week 4, Week 12, Week 24, Week 36 and Week 48) will be summarized descriptively for the subset of the participants achieving HbsAg seroclearance at any time before or at that given timepoint by cohort.

Cross-tabulations overtime of quantitative versus qualitative anti-HBs values will also be presented.

#### **5.4.2.2.3. Liver Stiffness Measurements**

Severity of liver disease at the end of consolidation phase and follow-up versus baseline will be evaluated by the changes in fibrosis according to Fibroscan liver stiffness measurements.

The changes from baseline at end of consolidation phase and end of follow-up will be summarized using descriptive statistics (n, mean, SE, 90% CI, median, minimum, maximum) by cohort

At each assessment time point, a frequency distribution of severity scores will be produced by cohort. A graphical display will also illustrate the findings.

#### **5.4.2.3. Endpoints for Correlation**

##### **5.4.2.3.1. Association Between Baseline Characteristics/Viral Blood Markers and Selected Efficacy Variables**

Correlations will be evaluated graphically using scatter plots, and heat maps displaying such potential associations by cohort and/or selected subgroups.

The following correlation coefficients will be calculated for the different correlation scenarios:

- Pearson's correlation coefficient for two continuous variables.
- Phi correlation coefficient for two binary variables.
- Point biserial correlation coefficient for one binary variable and one continuous variable.

## **6. SAFETY**

All safety analyses will be performed using the safety analysis set. All assessments will be presented by analysis phase and cohort for safety analysis set. All summaries will be only descriptive, and no inferential methods will be used for safety.

Safety and tolerability will be assessed by evaluating treatment emergent-adverse events (TEAEs), physical examinations, vital signs measurements, clinical laboratory tests (including hematology, blood biochemistry, blood coagulation, and urinalysis), and ECGs.

Continuous parameters will be summarized using the following statistics: number of observations, mean, standard deviation (SD), standard error (SE), minimum, median and maximum, unless specified otherwise. Frequencies and percentages will be used for summarizing categorical (discrete) data.

### **6.1. Adverse Events**

#### **6.1.1. Definitions**

The verbatim terms used in the CRF by investigators to identify adverse events will be coded using the Medical Dictionary for Regulatory Activities (MedDRA version 21.1 or higher). Treatment-emergent Aes (TEAE) are all Aes with a start date on or after the first administration of study

treatment or any ongoing event that worsens in severity, intensity or frequency after the first administration of study treatment. If the event date and/or resolution date is recorded as partial or completely missing, then the imputation rules described in Section 2.6.1 will apply.

### 6.1.2. Analysis Methods

The adverse events will be summarized by cohort and by analysis phase. Adverse events will be allocated to phases based on their start date. If the start date of an event falls between (or on) the start and stop date of an analysis phase, the AE will be attributed to that phase (treatment-emergent principle). For imputation of partially/fully missing dates please see Section 2.6.1. In case of a completely missing start date, the event is allocated to the induction study intervention phase, except if the end date of the AE falls before the first administration of study treatment in induction phase (Induction Day 1).

An overview table will summarize the incidence of TEAEs classified in the following categories: Aes, serious Aes, related Aes, Aes leading to treatment discontinuation, and fatal Aes by presenting by the number and percentage of participants who experienced at least one of such AE. The overview Aes table will be also presented stratified by the subgroup of interests identified in Section 2.5.2.

AE relationship to study treatment is grouped into either related or not related category. A related AE is defined as with possible, probable, or very likely relationship with study treatment; not related, otherwise.

All adverse events will be presented in a descending order by incidence based on all participants (Total column). The following TEAEs tables will be included in the analysis:

- All TEAEs
- Serious TEAEs
- At least grade 3 TEAEs
- At least grade 2 TEAEs and related
- TEAEs leading to treatment discontinuation
- Related TEAEs

All serious TEAE, related TEAE, TEAE leading to death, TEAE leading to treatment or study discontinuation, TEAE of at least grade 3, or adverse events of special interest (AESIs) will be listed separately. Listings will include all information collected on the Adverse Event CRF pages (e.g. information on time of onset, duration of events, time of resolution, concomitant therapies and relationship to study treatment).

For participants reporting rash, a listing with specific grade will be provided.

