- kk. PBMC samples will be collected at selected sites only. Additional PBMC samples may be taken in case of ALT flares, upon discussion with the sponsor, and may require an unscheduled visit.
- II. These samples are optional and will only be collected from participants who consent separately to this component of the study. The pharmacogenomic (DNA) sample should preferably be collected at baseline.
- mm. Adverse events and concomitant medications will be monitored from the time a signed and dated ISA ICF is obtained until completion of the participant's last ISA related procedure.
- nn. Exclusion criterion A25 regarding contraindications to the use of PegIFN α2a needs to be checked again at the end of the induction phase prior to the first dose of PegIFN α2a. If a participant's clinical status changes (including any available laboratory results or receipt of additional medical records) after screening but before the first dose of PegIFN α2a is given such that he or she meets exclusion criterion A25, then the participant should continue their study intervention until completion of the consolidation phase without the addition of PegIFN α2a.
- oo. The liver ultrasound does not need to be repeated at baseline if it was done at screening or within 6 months prior to screening.

- pp. As of Protocol Amendment 6, new participants will enroll without randomization to receive JNJ 3989+NA for 36 weeks (induction phase) and will then enter the 12 week consolidation phase during which they will have PegIFN  $\alpha$ 2a added to their treatment regimen.
- qq. Includes close monitoring for neuropsychiatric adverse events during the PegIFN α2a treatment period. Participants who develop a neuropsychiatric adverse event during PegIFN α2a treatment, will be monitored closely until the neuropsychiatric adverse event resolves, with frequent (at least weekly) follow up phone calls.
- rr. Most participants enrolled before Protocol Amendment 6 was in effect, have received JNJ 6379 as part of their study intervention. Dispensation of JNJ 6379 stopped immediately with the removal of JNJ 6379 as study intervention through an urgent safety measure. Participants have to return JNJ 6379 tablets to the site at the next scheduled visit.

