- The participant has confirmed ≥Grade 3 hematologic abnormalities as described in Section 8.3.6.4, Hematologic abnormalities.

*Note:* The grades are based on the DAIDS Toxicity Grading Scale (see Section 10.9, Appendix 9, DAIDS Table).

In addition, PegIFN- $\alpha$ 2a during consolidation phase must immediately be discontinued for any of the following reasons:

- Participant has platelet count <25,000 cells/mm^3
- Participant has ANC <500 cells/mm^3 Note: PegIFN-α2a treatment can be restarted when ANC values return to more than 1,000 cells/mm^3 (see details in Section 6.6, Dose Modification)
- Participant develops evidence of hepatic decompensation during treatment, or ALT increase clinically significant or accompanied by direct bilirubin increase
- Participant develops thyroid disorders or diabetes during treatment and cannot be controlled with medication
- Participant develops new or worsening ophthalmologic disorders
- Participant develops any deterioration of cardiovascular status
- Participant develops serious, acute hypersensitivity reaction (e.g., urticaria, angioedema, bronchoconstriction, anaphylaxis)
- Participant develops serious infection (bacterial, viral, fungal) and sepsis
- Participant develops persistent or unexplained pulmonary infiltrates or pulmonary function impairment
- Participant with onset or worsening of psoriatic lesion
- Participant develops moderate or severe depression, or other psychiatric symptoms (for mild depression, treatment discontinuation may be considered)

*Note:* Participants who develop a neuropsychiatric AE during PegIFN- $\alpha$ 2a treatment, will be monitored closely until the neuropsychiatric AE resolves, with frequent (at least weekly) follow-up phone calls.

- Participant develops colitis symptoms (such as but not limited to abdominal pain, bloody diarrhea, and fever)
- Participant develops symptoms or signs suggestive of pancreatitis

For participants who prematurely discontinue PegIFN- $\alpha$ 2a, treatment with PegIFN- $\alpha$ 2a may be restarted according to the recommendations from the locally approved prescribing information for PegIFN- $\alpha$ 2a.

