## 2. GENERAL ANALYSIS DEFINITIONS

The SAP will use throughout the document the following definitions:

The term “**induction phase**” corresponds to the first treatment phase of the study starting with enrollment into induction phase of flexible duration of 36-60 weeks (inclusive) for Cohort 1 and starting with randomization or enrollment into the induction phase of a fixed duration of 36 weeks for Cohort 2.

The term “**consolidation phase**” corresponds to the second treatment phase of the study starting with the first PegIFN- $\alpha$ 2a intake with a fixed duration of 12 weeks for both cohorts.

- *Study treatment/intervention* refers to: JNJ-3989, JNJ-6379, NA (TeD, or TAF) and PegIFN- $\alpha$ 2a prior to Protocol Amendment #6; JNJ-3989, NA (TeD, or TAF) and PegIFN- $\alpha$ 2a as of Protocol Amendment #6.
- *Study agent* refers to: JNJ-3989, JNJ-6379, and PegIFN- $\alpha$ 2a prior to Protocol Amendment #6; JNJ-3989 and PegIFN- $\alpha$ 2a as of Protocol Amendment #6.

- *Study intervention arm* will be specified with Cohort 1 and Cohort 2 which are distinguished between participants enrolled prior to or after Protocol Amendment #6 as the Protocol Amendment #5 was not implemented due to the USM and no participants will be receiving Protocol Amendment #5 treatment. All participants enrolled prior to the Protocol Amendment #5 will comprise Cohort 1. The participants enrolled after approval of Amendment #6 who will comprise Cohort 2. The Study intervention arm in the SAP will be
  - Cohort 1:
    - JNJ-3989 + JNJ-6379 + NA + PegIFN- $\alpha$ 2a
    - JNJ-3989 + NA + PegIFN- $\alpha$ 2a
  - Cohort 2:
    - JNJ-3989 + NA + PegIFN- $\alpha$ 2a

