**Table 1: Analysis Phases Start and End Dates**

Analysis phase	Start date	End date
Screening	The date of signing the informed consent	1 day before the first study agent intake (excluding PegIFN- $\alpha$ 2a)
Induction phase	Cohort1: Date of first study agent intake (excluding PegIFN- $\alpha$ 2a)	Cohort1: Participants who are randomized: Min{Max[Date of first PegIFN- $\alpha$ 2a intake, Date of randomization] -1 day, cut-off date b }  Participants who are not randomized but receive PegIFN-<math>\alpha</math>2a: Min[Date of first PegIFN- $\alpha$ 2a intake-1 day, cut-off date b ]  Participants who are not randomized and did not receive PegIFN-<math>\alpha</math>2a: Min{Min[JNJ-3989 discontinuation date a , early study withdrawal visit date, max(Week 36 to 60 visit date from induction phase)] + 5 days a , cut-off date b }
	Cohort 2: Date of first study agent intake (excluding PegIFN- $\alpha$ 2a)	Cohort 2: Participants who receive PegIFN-<math>\alpha</math>2a: Min[Date of first PegIFN- $\alpha$ 2a intake – 1 day, cut-off date b ]  Participants who did not receive PegIFN-<math>\alpha</math>2a: Min{Min[JNJ-3989 discontinuation date a , early study withdrawal visit date, Week 36 visit date from induction phase] + 5 days a , cut-off date b }

Analysis phase	Start date	End date
Consolidation phase	Cohort 1: Participants who receive PegIFN- <math>\alpha</math>2a: Date of first PegIFN- $\alpha$ 2a intake  Participants who did not receive PegIFN- <math>\alpha</math>2a: date of any study agent intake after Max[Week 36 to 60 visit date]  Otherwise: Missing	Cohort1: Participants who did not withdraw from the study prior to the Consolidation Week (CW) 12 visit date: Min{Max[last intake date of any study agent (excluding NA), CW c 12], JNJ-3989 discontinuation date a } + 5 days a or cut-off date b , whichever occurs first  Participants who withdrew from the study prior to the Consolidation Week 12 visit date: Min[JNJ-3989 discontinuation date a , early study withdrawal visit date] + 5 days a or cut-off date b , whichever occurs first  Otherwise: Missing

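### The SAP tabulates each adverse event only in the phase where it started, so an event kept as one record that worsens on PegIFN is not counted in Consolidation

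*SAP*

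**What the plan says.** **Treatment emergence.** Besides events that start on or after first dose, SAP 6.1.1 counts "any ongoing event that worsens in severity, intensity or frequency after the first administration of study treatment". The reference point is the first dose of any study treatment, not the start of a phase or the first PegIFN dose.

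**Phase allocation.** SAP 6.1.2 states "Adverse events will be allocated to phases based on their start date". When the start date lies within a phase, "the AE will be attributed to that phase (treatment-emergent principle" applies. The one stated exception is a wholly missing start date, which goes to Induction unless the event ended before Induction Day 1.

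**Presentation.** SAP section 6 states "All assessments will be presented by analysis phase and cohort for safety analysis set". SAP 6.1.2 lists tables of all, serious, grade 3 or higher, related, and treatment-stopping TEAEs. SAP 6.1.3 summarises AESIs by phase. None of these has its own allocation rule.

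**Phase boundaries.** SAP Table 1 makes Screening an analysis phase that ends the day before the first study agent. In SAP section 2 the consolidation phase "corresponds to the second treatment phase of the study starting with the first PegIFN" intake, and in Table 1 Induction ends the day before it.

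**Collection and stopping.** The protocol's Schedule of Activities footnotes state "Adverse events and concomitant medications will be monitored from the time a signed and dated ISA ICF is obtained", so screening-onset events are captured. Protocol 7.1 includes "Participant with onset or worsening of psoriatic lesion" among the reasons to stop PegIFN.

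**The concern.** The definition of a TEAE recognises worsening, but the rule that puts the TEAE in a table column does not. Grade, seriousness and action taken belong to the event record, so they go to the onset phase even when they arose later.

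This matters because, as of Protocol Amendment 6, there is a single arm. With no concurrent comparator, the contrast between Induction (JNJ-3989+NA) and Consolidation (the same plus PegIFN) is how a reader of the AE tables would judge what adding PegIFN did. An event that began mildly in Induction and became severe on PegIFN would show as a severe event in a phase when no PegIFN was given. If PegIFN was stopped for it, the stop would be tabulated there too. Protocol 7.1 allows PegIFN to stop while JNJ-3989 continues, so that placement could also mislead about which drug was stopped.

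**Working it through.** The documents give no figure that depends on this rule, so there is none to reproduce. The check applies the written rule to the Cohort 2 phase boundaries.

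**Inputs.** Induction starts on Day 1 (SAP Table 1). First PegIFN is taken at the Week 36 target, Day 253 (SAP Table 2). Consolidation Week 12 has target consolidation day 85, which is study day 253 + 84 = 337. Three hypothetical events:

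| Event | Onset | Worsening | Phase under SAP 6.1.2 | Phase where it worsened |
|---|---|---|---|---|
| Present at screening, grade 3 and PegIFN stopped | Day -10 | Day 270 | Screening | Consolidation |
| Grade 1 in Induction, grade 3 and PegIFN stopped | Day 200 | Day 270 | Induction | Consolidation |
| New on PegIFN | Day 270 | Day 270 | Consolidation | Consolidation |

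The first two are TEAEs under SAP 6.1.1, and neither is in Consolidation. For the first, the SAP does not say whether a Screening column would be printed or the event would drop out of the by-phase TEAE tables. Either way it is not in the phase where it worsened. The wholly-missing-date exception does not help, since it also sends events to Induction.

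**Size per participant.** Shift in phase incidence = 100 × k / n, where k is the number of participants whose event is misplaced. The documents do not give k, so the range is an assumption.

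- n = 33 (Cohort 2 target): k = 1 gives 100/33 = 3.0 points; k = 5 gives 500/33 = 15.2 points.
- n = 30 (after the assumed 10% dropout): 3.3 to 16.7 points.
- n = 60 (both cohorts): 1.7 to 8.3 points.

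**How the SAP treats other data.** SAP 4.4 lets a concomitant medication fall in one or several phases according to its start and end dates. SAP 6.2.1, 6.2.4.1 and 6.2.5.1 derive the worst laboratory, ECG and vital-sign result within each phase. AEs have no equivalent.

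**The case against.** Several points on the other side stand.

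- **The recording convention is not visible.** The effect needs a worsened event to stay one record. AE procedures are in Attachment 4 of the Master Protocol, which is not among these documents. If a worsening opens a new record, the effect largely disappears. The wording of SAP 6.1.1 suggests a single continuing record, but it defines emergence relative to first dose and does not settle how worsening is recorded.
- **Other displays cover the PegIFN period.** A neutrophil, platelet or ALT abnormality that worsens on PegIFN appears in Consolidation through the within-phase worst grade. SAP 5.3.2.2.1 summarises ALT change from the consolidation reference point. SAP 4.1 summarises treatment-discontinuation reasons by phase and lists discontinuation dates. AE listings show onset and duration. A reader might infer that the AE tables are the only display isolating PegIFN; they are not.
- **The pool of events is reduced.** Exclusion criterion A25 covers pre-existing ophthalmologic disorders, bone marrow suppression, and uncontrolled thyroid and psychiatric disorders. It is checked again before PegIFN, and anyone who then meets it continues without PegIFN. Criterion M13 excludes clinically significant skin disease needing regular or periodic treatment at entry. Induction-onset psoriasis and other events outside A25 remain possible.
- **Counting each event once is a legitimate choice.** It avoids double counting, and the safety analysis is descriptive.

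A reader might also infer an established bias in PegIFN's favour, or a large understatement of severe events in Consolidation. The documents support neither. They give no event counts. The rule also keeps an event that starts on PegIFN and worsens in follow-up in Consolidation, at its later grade. And Consolidation contains JNJ-3989 and NA as well, so no phase table attributes events to PegIFN alone.

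What survives is the gap itself: no section of the SAP says where a TEAE that worsens in a later phase is counted.

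**Conclusion.** The point holds, conditionally and within limits. If a worsened AE stays one record with its original start date, SAP 6.1.1 and 6.1.2 together place a screening-onset TEAE in a pre-drug phase, and an induction-onset event that worsens on PegIFN in Induction with its later grade and action taken. The by-phase tables mainly affected are those of clinical AEs: all, grade 3 or higher, serious, and leading to discontinuation. The discontinuation table could then disagree with the treatment-disposition summary over the phase of the same PegIFN stop. Overall TEAE totals are unaffected.

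The number of affected events is unknown and may be small. What can be stated is the unit effect, about 3.0 percentage points of phase incidence per affected participant at n=33. The primary efficacy analysis is untouched. It is still worth correcting, because the by-phase contrast carries much of the tolerability reading in a single-arm study and the correction is cheap.

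**What to change.** Amend SAP 6.1.2 as follows.

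1. Keep start-date allocation for new events.
2. Add that a TEAE which started in an earlier phase, Screening included, and which worsens, becomes serious or leads to stopping a study drug in a later phase is also counted in that later phase, at the grade reached there. Count it in the all-TEAE row as well as the category row, so that no event sits in a category without being in the total.
3. Report grade and action taken in the phase where they occurred. For discontinuations, use the date the drug was stopped.
4. State the CRF convention for worsening. If each worsening opens a new record with its own start date, say so; the start-date rule then suffices and items 2 and 3 are not needed.

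The cost is one derivation rule and a footnote that an event can appear in two phases. The worsening part needs either a date of worsening or a new record in the CRF. If the CRF holds neither, the discontinuation part can still be applied, because SAP 4.1 already lists discontinuation dates. The SAP should then state that worsening across phases cannot be tabulated. No clinical procedure changes.
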